6.2.6 Visit 1 (2 weeks)

- Assessment for any adverse events (AEs) since the previous visit, including documentation and reporting as applicable
- Radiographs
- Cast removal for the titanium elastic nail (TEN) group, if applicable
- Clinical examination and outcome assessments as described in Section 7
- Source data verification and entry into the eCRF
- Scheduling of the next visit
- Appointment for the next visit

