6.3.4.3 Postoperative care and discharge

Wounds are closed and dressed according to standard practice. A circumferential above-elbow cast is applied for the duration specified by the randomized treatment package. Discharge occurs when the child is clinically well and postoperative pain is controlled, typically on the same day or the day after surgery, in accordance with local routines. No formalized physiotherapy is routinely prescribed; participants and parents receive oral and written instructions regarding mobilization and home exercises.

Follow-up assessments are conducted according to the schedule described in Section 6.2.

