Unblinding may be performed only when knowledge of the allocated implant is deemed necessary for urgent clinical management. Emergency unblinding will be performed by the PI, documented in the eCRF (date, reason, person unblinded, and who was informed), and reported to the sponsor.

6.3.7.4 *Blinded groups*

The following parties will be blinded to treatment allocation:

- Participants and parents will be blinded to implant type. Families will be informed preoperatively that postoperative immobilization duration may vary between 2–4 weeks based on radiographic assessment, and they will not be informed that immobilization duration differs systematically between the randomized interventions. As the implant is not externally visible after cast removal and implant-specific radiographic features are concealed for research assessments (Section 7.1), there is no direct method for participants and parents to identify allocation during follow-up.
- Postoperative ward/clinic caregivers and staff involved in routine care.
- Outcome assessors and data collectors, including:
 - Clinicians performing follow-up assessments
 - Radiologists and orthopedic surgeons reviewing radiographs (using edited, de-identified images; Section 7.1)
 - Occupational therapists / hand therapists performing functional assessments
- Statistician/data analyst, who will receive a dataset with groups coded (e.g., Group A/B) and will remain blinded until database lock and completion of the prespecified primary analysis.

6.3.7.5 *Preventing inadvertent unblinding*

To reduce inadvertent disclosure, the study team will implement the following safeguards:

- Use of standardized note templates for postoperative notes and discharge summaries.
- Clear instruction to staff not to document implant type in routine follow-up notes that are accessible to blinded parties.
- If implant type must be referenced for clinical reasons before planned unblinding, it will be documented and handled according to the emergency unblinding procedure.

6.3.7.6 *Assessment of blinding success*

Blinding success will be assessed immediately prior to participant/parent unblinding at the 6-month follow-up visit. Participants/parents will be asked to guess the allocation (“bioabsorbable”, “titanium”, or “don’t know”) and if they specify an implant, they will be asked why they chose that implant. The proportion of correct guesses and reasons (and proportion choosing “don’t know”) will be summarized by randomized group.

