6.3.8 **Postoperative care**

Following surgery, a circumferential above-elbow cast is applied. The patient will be observed and/or admitted to the pediatric ward as clinically indicated until the effect of the peripheral nerve block (PNB) has subsided and discharge criteria are met. The patient is encouraged to mobilize the shoulder and fingers as soon as possible and to keep the arm elevated for the first few days. Daily activities may be resumed as tolerated. Return to sports will be discussed individually at the 3-month follow-up visit in accordance with standard of care.

Before discharge, a standardized discharge and follow-up plan will be provided.

In the investigational group (BIN), all patients will remain in a cast for 4 weeks. In the comparator group (TEN), cast removal is planned at the 2-week follow-up visit.

Any postoperative care not specifically described in this protocol will be provided according to standard of care at the study site and described in a specific SOP.

6.3.9 **Non-operative treatment**

If the fracture is successfully reduced by closed manipulation prior to skin incision and is considered eligible for non-operative management, the patient will be included in an exploratory prospective non-operative cohort. Based on our pilot experience, the proportion of successful closed reductions is anticipated to be approximately 15%.

6.3.9.1 *Eligibility for non-operative management*

Fractures are considered eligible for non-operative treatment when, after reduction, the fracture is:

- not displaced by more than 50% of the bone width, and
- not angulated by more than 10° in any plane.

The decision to manage the fracture non-operatively is at the treating surgeon’s discretion and follows standard of care.

6.3.9.2 *Follow-up and conversion to surgery*

Participants in the non-operative cohort will have a radiographic follow-up at 1 week. Thereafter, they will follow the same follow-up schedule and outcome assessments as the randomized groups (Section 6.2). Fracture healing is typically sufficient to allow cast removal after 6–8 weeks.

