8.3.2 Analysis populations

In non-inferiority trials, intention-to-treat (ITT) analyses may be biased toward non-inferiority due to treatment cross-over and non-adherence. We intend to analyze both the per-protocol (PP) and ITT populations. The primary non-inferiority analysis will be performed in the PP population. A supportive analysis will be performed in the ITT population. Non-inferiority will be considered robust if conclusions are consistent in both PP and ITT analyses. We suspect very few cases will cross over. We suspect to find similar results in both groups and a discrepancy would warrant close examination of the results.

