8.3.3.1 Major protocol deviations

Major protocol deviations resulting in exclusion from the PP population will include:

- (1) implantation of a non-allocated device or cross-over to the alternate trial implant
- (2) failure to undergo intramedullary fixation after randomization
- (3) major deviations in post-operative immobilization that alter the treatment package (e.g., cast duration differing by more than ± 7 days from the planned duration, unless medically indicated and documented)
- (4) healing-related reoperation prior to reaching the radiographic healing threshold (e.g., revision fixation for loss of reduction or refracture)
- (5) missing radiographic assessments such that the healing interval cannot be determined (e.g., absence of any post-operative radiograph beyond the initial post-operative imaging or missing consecutive assessments preventing interval definition).

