9.3.3 Fracture re-angulation

There may be an increased risk of fracture re-angulation when using BIN due to the greater flexibility of the implant. This risk is mitigated by immobilization in a circumferential above-elbow cast for 4 weeks, in accordance with the Technique Guide for the Activa IM-Nail™.

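### Section 6.3.7.4 gives families a radiographic reason for a cast time that the plan sets by arm, and calls clinic staff blinded although casts come off by arm and clinical films are unedited

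*Protocol*

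**What the plan says.** Section 6.3.7.4 of the Protocol describes what families hear before surgery: "Families will be informed preoperatively that postoperative immobilization duration may vary between 2–4 weeks based on radiographic assessment". The same sentence adds that they will not be told that immobilization differs systematically between the arms.

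The treatment sections give a different basis for the duration:

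- Section 6.3.4.3: "A circumferential above-elbow cast is applied for the duration specified by the randomized treatment package". Sections 6.3 and 6.3.4.2 define those packages as BIN with 4 weeks of casting and TEN with 2 weeks.
- Section 6.3.8: "In the investigational group (BIN), all patients will remain in a cast for 4 weeks" and "In the comparator group (TEN), cast removal is planned at the 2-week follow-up visit".
- Section 6.2.6, Visit 1: "Cast removal for the titanium elastic nail (TEN) group, if applicable". Section 6.2.7 has the matching line for BIN at Visit 2, and the study schedule table lists removal by group.
- Section 9.3.3, on re-angulation with BIN: "This risk is mitigated by immobilization in a circumferential above-elbow cast for 4 weeks". Section 9.5 repeats this.

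On blinding, section 6.3.7 conceals allocation from postoperative clinical staff and outcome assessors. Section 6.3.7.4 names ward and clinic caregivers and the clinicians who do follow-up assessments. Section 6.3.7.2 says that clinical care relies on the unedited radiographs.

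**The concern.** Two statements in section 6.3.7.4 do not fit the rest of the protocol.

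The first is the reason given to families. Withholding the arm difference is an openly stated blinding measure and is not the objection. The objection is that a specific reason is offered, a reading of the radiograph, which is not how the plan sets cast duration.

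The second is the list of blinded parties. Staff asked to take casts off one arm at 2 weeks and the other at 4 weeks can work out the arm from cast status. Staff who look at the clinical films can see it directly. What is at stake is how outcomes measured in clinic should be read, such as range of motion and grip strength (section 7.2.10). If the report calls these blinded without qualification, it claims more than the design delivers.

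**Working it through.** No figure in the plan bears on this point, so the check is mainly a comparison of text.

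**1. Is there a radiographic rule for cast removal in the randomised arms?** None appears in sections 6.2.6, 6.2.7, 6.3.4 or 6.3.8. Where the protocol wants a radiograph to drive conduct, it says so: in sections 6.2.8 and 6.2.9 an mRUS below 11 in any fractured bone triggers an extra visit. Nothing comparable is attached to the cast.

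**2. Do other parts treat duration as fixed by arm?** Yes. Section 8.3.3.1 lists among major deviations "cast duration differing by more than ± 7 days from the planned duration, unless medically indicated and documented". Around each arm's planned duration this gives:

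- TEN: 2 × 7 = 14 days; 14 − 7 = 7 to 14 + 7 = 21 days.
- BIN: 4 × 7 = 28 days; 28 − 7 = 21 to 28 + 7 = 35 days.

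The two windows share only day 21. A duration set case by case from the radiograph, anywhere in 2 to 4 weeks, would not be defined this way. The risk sections agree, because for BIN the 4 weeks is the named control for re-angulation.

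**3. Does the flexible wording make the radiograph the basis?** No. The qualifier on removal at Visits 1 and 2, the word planned for TEN, and the medical exception in section 8.3.3.1 allow individual departures. They do not set the duration. For BIN, section 6.3.8 refers to all patients.

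**4. Can the listed staff stay blinded?** There are two routes to the arm:

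- *Cast status.* With 30 per group, the plan at Visit 1 is cast off in 30 TEN children and cast kept in 30 BIN children. Individual exceptions aside, whether the cast stays on tells staff the arm.
- *Clinical films.* Radiographs are taken at both visits. Section 7.1.1.4 says titanium nails are radiopaque and BIN are largely radiolucent apart from the tip. Masking applies to the research copies only. This route is the more direct one and does not depend on the cast.

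The safeguards in section 6.3.7.5 concern notes and documentation and close neither route.

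**5. Who sets the removal date?** Section 6.3.7 gives the unblinded personnel device logistics and the planning of titanium nail removal, and keeps them out of postoperative assessment. Nobody in this document is assigned to set the cast date.

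**The case against.** The strongest reply is that the quoted words are a message to families, not an instruction to staff. The rest of the sentence acknowledges that duration differs by arm, so anyone working from the protocol knows the real rule. That stands. A reader might infer that a BIN child could be taken out of the cast at 2 weeks on a radiograph and lose the re-angulation control. The documents do not support this: no section tells staff to act on the radiograph, and several tell them to follow the package.

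A reader might also infer a loss of per-protocol patients, since "The primary non-inferiority analysis will be performed in the PP population". That depends on the same unsupported scenario, and a cast change on radiographic grounds could qualify as the medically indicated exception. The number of casts that would be moved cannot be derived from the document.

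The second reply is that operational detail sits in SOPs. Sections 6.3.4 and 6.3.8 say so, and section 6.3.7.1 names follow-up scheduling as a disclosure route to be guarded. An SOP may therefore already have an unblinded person issue the removal date. This limits the staffing point to the present document. It does not correct the reason written into section 6.3.7.4, and it does not stop staff who see the cast or the unedited films from inferring the arm.

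Third, the qualifier on removal applies in both arms and radiographs are taken at the same visits, so a radiographic check at removal is not foreign to the plan. That is fair, but such a check is not what determines 2 or 4 weeks.

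**Conclusion.** The point holds and is minor. The reason to be given to all 60 randomised families does not match the plan. The claim that clinic staff and follow-up clinicians are blinded holds at best in part.

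It would be wrong to infer that the primary endpoint loses its protection. Healing is scored on masked, de-identified films by two independent blinded reviewers (sections 7.1.1.4 and 7.1.1.5), and this point does not touch that arrangement. The consequence is confined to the accuracy of the family explanation and to how clinic-assessed secondary outcomes are interpreted up to the 6-month unblinding. How much, if at all, knowledge of the arm would shift those outcomes cannot be worked out from the document.

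The conclusion assumes that clinic staff at Visits 1 and 2 see cast status or the clinical films in ordinary care. An assessor who sees neither, such as a therapist testing at 12 weeks, could remain blinded. The family information pages and SOPs are not in our copy, so their wording could not be checked.

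**What to change.** 1. Section 6.3.7.4: delete the radiographic reason and tell families only that the cast stays on for 2 to 4 weeks. Make the same change in the family information if the phrase appears there.
2. Sections 6.3.7 and 6.3.7.4: state that clinic staff and follow-up clinicians who see cast status or unedited films can infer the arm; that clinic-assessed secondary outcomes up to unblinding are interpreted as partially blinded; and that the primary endpoint remains protected by masked reading.
3. Section 6.3.8: have an already unblinded person with no assessment role, for example the operating surgeon or trial coordinator, set each removal date by package. If an SOP already provides this, a reference to it is enough.

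The cost is one deleted phrase, a few sentences and an amendment submitted to the ethics committee. Families given no reason may ask why the cast stays on, so staff need one neutral reply. The blinding claim becomes narrower. Randomisation, endpoint, model and sample size are unchanged.

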7.1 Primary outcome

Time to fracture healing (weeks), defined as the time from surgery/randomization (Day 0) to the first postoperative radiographic assessment meeting the prespecified healing criterion in all fractured bones as described in 7.1.2.3.

7.1.1 Time to fracture healing

As described in Section 4.2, fracture repair is a complex biological process and objective assessment in clinical trials is challenging [45]. Healing based on plain radiographs has historically been largely subjective. Whelan et al. developed the Radiographic Union Score (RUS) to quantify healing in tibial fractures based on callus formation and visibility of the fracture line [46]. RUS has since been shown to be reliable and repeatable, including anatomical sites beyond the tibia [47–49], and to correlate with biomechanical properties of healing [50]. To improve clarity and reduce ambiguity in scoring, a modified RUS (mRUS) has been proposed, defining callus as bridging versus non-bridging [51].

7.1.1.1 Definition of time-to-healing (primary time origin)

Time-to-healing will be defined as the time from the date of surgery/randomization (Day 0) to the first postoperative radiographic assessment meeting the pre-specified healing threshold in all fractured bones. For patients with fractures of both radius and ulna, the endpoint is met when the healing threshold is achieved for both bones; for isolated single-bone fractures, the endpoint is met when the fractured bone reaches the threshold. Injury date will be recorded for all participants. As sensitivity analyses, time-to-healing will also be calculated from the date of injury, and analyses may adjust for the injury-to-surgery interval to assess robustness.

7.1.1.2 Radiographic assessment method (mRUS)

Healing will be assessed on standard plain anteroposterior (AP) and lateral radiographs. For each fractured bone, four cortices are scored (1–4) and summed to yield an mRUS from 4 (not healed) to 16 (fully healed). Scoring of each cortex is defined as follows:

- visible fracture line and no callus is scored 1 (Figure 2.1)
- non-bridging callus with visible fracture line is scored 2 (Figure 2.2)
- bridging callus with visible fracture line is scored 3 (Figure 2.3)
- bridging callus with no visible fracture line is scored 4 (Figure 2.4)

The sum of the four cortices constitutes the mRUS for that bone. Based on prior work, a threshold of mRUS ≥ 11 is considered consistent with radiographic union and mRUS ≥ 13 with definite union [51].

[figure not shown]

Figure 2 - Calculation of mRUS. A cortex with visible fracture line and no callus is scored one (1), with non-bridging callus and a visible fracture line is scored two (2), with bridging callus and a fracture line is scored three (3) and with bridging callus and no visible fracture line is scored four (4). The sum of the four scores gives the mRUS.

7.1.1.3 Radiographic healing threshold (primary endpoint)

Healing will be defined as mRUS ≥ 11 for the fractured bone with bridging callus (cortex score ≥ 3) present in at least three of four cortices, and no cortex with score of 1. For combined radius and ulna fractures, the endpoint is met when both bones meet the healing threshold on the same radiographic assessment.

This threshold operationalizes union as bridging callus in ≥ 3 cortices (consistent with established radiographic union definitions) while limiting premature classification by requiring absence of cortices with no callus.

[figure not shown]
Definite union (supportive threshold). As a supportive radiographic definition, definite union will be defined as mRUS ≥ 13 for the fractured bone, which corresponds to bridging callus in all four cortices with at least one cortex demonstrating absence of a visible fracture line (cortex score 4). This more stringent threshold is expected to occur later in the healing trajectory and will therefore be used for pre-specified sensitivity analyses of the primary time-to-healing endpoint and for descriptive comparison of healing profiles between groups, rather than as the primary event definition.

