Hypothesis	Time to radiographic healing after BIN is non-inferior to that after TEN.
Primary outcome measure	
Time to radiographic healing, defined as time from surgery/randomization to achieving mRUS ≥ 11.
 
Healing is assessed on plain anteroposterior (AP) and mediolateral (ML) radiographs and objectively quantified using the modified Radiographic Union Score (mRUS).

Secondary outcome measure(s)	
 • Range of motion (degrees) measured by goniometer • Grip strength measured by dynamometer • Faces Pain Scale – Revised (FPS-R) • Questions from the Nationwide Survey of Patient Experiences • Complications, reoperations, and adverse events (AEs) related to the procedure and/or implants • Pediatric and Danish version of EQ-5D (EQ-5D-Y) • Motor function assessment: Movement Assessment Battery for Children – Third Edition (MABC-3), Manual Dexterity domain

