
Statistical considerations and estimated enrollment
	
A statistician from the University of Copenhagen contributed to the trial design, including selection of statistical methods and the sample size/power calculations.
 
This is a randomized, parallel-group, non-inferiority study with equal allocation (1:1). The primary endpoint is time to healing, defined as the time from surgery to achieving mRUS ≥ 11.
 
The non-inferiority margin was selected based on clinical judgement and available evidence and was further contextualized by parent input from the pilot cohort regarding the maximum acceptable additional weeks of activity restriction (beyond the usual 6 weeks) in exchange for avoiding a second implant removal operation. We set the non-inferiority margin $\Delta = 3$ weeks.
 
With a non-inferiority margin $\Delta = 3$ weeks, the hypotheses are: $H_0: \theta \geq \Delta$ (BIN is inferior to TEN by ≥ 3.0 weeks) $H_1: \theta < \Delta$ (BIN is non-inferior to TEN)
 
  
 Sample size	
   
 Significance level	0.025	
 
 Power (1-β)	0.9	
 
 Ratio of sample size	1:1	
 
 Standard deviation (SD)	3 weeks	
 
 Non-inferiority margin (Δ)	3 weeks	
 
 Loss to follow-up/withdrawal (%)	5	
 
 Intercurrent events (%)	5	
 
 Result	
 
 Sample size per group	22	
 
 Sample size per group incl. attrition	25	
 
 Total sample size incl. attrition	50	
  
 
The required sample size is 25 per group; to ensure operational robustness we will enroll 30 per group (total 60).
	Sample size		Significance level	0.025	Power (1- β)	0.9	Ratio of sample size	1:1	Standard deviation (SD)	3 weeks	Non-inferiority margin (Δ)	3 weeks	Loss to follow-up/withdrawal (%)	5	Intercurrent events (%)	5	Result		Sample size per group	22	Sample size per group incl. attrition	25	Total sample size incl. attrition	50
Sample size																									
Significance level	0.025																								
Power (1- β)	0.9																								
Ratio of sample size	1:1																								
Standard deviation (SD)	3 weeks																								
Non-inferiority margin (Δ)	3 weeks																								

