6.2.8 Visit 3 (6 weeks)

- Assessment for any adverse events (AEs) since the previous visit, including documentation and reporting as applicable
- Radiographs
- Clinical examination and outcome assessments as described in Section 7
- Source data verification and entry into the eCRF
- Scheduling of the next visit:
 - If bone healing is not sufficient, defined as an mRUS < 11 in any fractured bone, a follow-up visit will be scheduled at 8 weeks postoperatively.
 - If bone healing is sufficient (mRUS ≥ 11 in all fractured bones), the next visit will be scheduled at 3 months postoperatively.

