8.2 Sample size considerations

Sample size was calculated for a parallel-group, randomized (1:1), non-inferiority comparison of time to radiographic healing, defined as time from surgery/randomization to the first radiograph with mRUS ≥ 11 .

[figure not shown]

Figure 5 – Power table. To better appreciate the effects on sample size four standard deviations (SD) are plotted for five different power levels. The chosen SD and power are circled.

[figure not shown]

Figure 6 – Table to show sample size at 3 SD for 4 different non-inferior margins. The chosen margin and sample size are circled.

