8.2.2 Standard deviation

Due to limited evidence on the exact healing times of forearm fractures in children, the values are based on our pilot study, available literature [14,56] and our clinical expertise. In our pilot study of 18 fractures median time to healing with an mRUS of at least 11, was 8 weeks. We estimate that fractures heal to an mRUS of ≥ 11 at an average of 8 weeks with a SD of 3 weeks.

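### The primary healing event is defined in two ways that do not agree: a cortex rule in section 7.1.1.3, and a total mRUS of at least 11 in the synopsis, the sample-size section and the visit-scheduling rules

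*Protocol*

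**What the plan says.** Section 7.1.1.2 scores each of four cortices from 1 to 4 and defines mRUS as their plain sum, from 4 to 16.

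Section 7.1.1.3, which sets the primary endpoint, requires mRUS ≥ 11 "with bridging callus (cortex score ≥ 3) present in at least three of four cortices, and no cortex with score of 1". In a both-bone fracture, both bones must satisfy this on the same film.

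Other sections define the same endpoint, or act on it, by the total alone:

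- Synopsis, primary outcome: "Time to radiographic healing, defined as time from surgery/randomization to achieving mRUS ≥ 11".
- Synopsis, statistical considerations: "The primary endpoint is time to healing, defined as the time from surgery to achieving mRUS ≥ 11".
- Section 8.2: "defined as time from surgery/randomization to the first radiograph with mRUS ≥ 11".
- Section 8.2.2, pilot: "median time to healing with an mRUS of at least 11, was 8 weeks". The planning mean of 8 weeks and SD of 3 weeks are given for the same threshold.
- Section 6.2.8: "If bone healing is not sufficient, defined as an mRUS < 11 in any fractured bone, a follow-up visit will be scheduled at 8 weeks"; and "If bone healing is sufficient (mRUS ≥ 11 in all fractured bones), the next visit will be scheduled at 3 months postoperatively". Section 6.2.9 repeats this at week 8, and 6.2.10 makes the week-10 visit depend on it.

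Section 7.1 points to 7.1.2.3 for the criterion, but no such section exists. For definite union, 7.1.1.3 says of mRUS ≥ 13: "which corresponds to bridging callus in all four cortices with at least one cortex demonstrating absence of a visible fracture line".

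**The concern.** The protocol nowhere says that mRUS ≥ 11 is shorthand for the cortex rule, and 7.1.1.2 gives the total its own fixed meaning. If the two rules can disagree, a child may be treated as healed for scheduling although the primary event has not occurred. The 8- and 10-week films are then not taken, around the planned mean healing time of 8 weeks.

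That conflicts with section 7.3, which keeps follow-up films going until healing has been shown, and with section 8.3.6, which rests the interval-censored analysis on two-weekly films. Whether a film exists would also depend on a near-threshold reading of the outcome itself. Separately, the pilot median and planning SD might describe a different event from the one analysed.

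**Working it through.** **1. The plan's own sample size.** Inputs from 8.2: margin 3 weeks, SD 3 weeks, one-sided 0.025, power 90%, no true difference. n = 2·SD²·(z₀.₉₇₅ + z₀.₉₀)²/Δ² = 2·9·(1.960 + 1.282)²/9 = 21.01, rounded up to 22 per group. With 10% inflation, 22/0.90 = 24.4, rounded up to 25. Both stated figures reproduce.

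**2. Does the cortex rule imply the total?** Three cortices of at least 3 and none scored 1 give at least 3+3+3+2 = 11. So the cortex rule alone decides the event, and the total adds nothing to it.

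**3. Does the total imply the cortex rule?** Ignoring the order of the cortices, 15 score combinations total at least 11. Nine meet 7.1.1.3 and six do not:

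| Combination | Total | Why it fails 7.1.1.3 |
|---|---|---|
| 4-4-2-1 | 11 | two bridging cortices; one scored 1 |
| 4-3-3-1 | 11 | one scored 1 |
| 4-3-2-2 | 11 | two bridging cortices |
| 4-4-3-1 | 12 | one scored 1 |
| 4-4-2-2 | 12 | two bridging cortices |
| 4-4-4-1 | 13 | one scored 1 |

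At a total of exactly 11, only 3-3-3-2 passes. When no cortex scores 4, the only combinations reaching 11 are 3-3-3-2 and 3-3-3-3, and both pass. Disagreement therefore always needs a cortex scored 4.

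**4. Effect on the data.** Take a child with a fractured bone at 4-3-2-2 at week 6 and every fractured bone totalling at least 11. Under 6.2.8 the next film is at week 12, so the healing time lies in (6,12]. With two-weekly films it would lie in (6,8], (8,10] or (10,12]. The same pattern first seen at week 8 gives (8,12]. If healing is dated to the first qualifying film, as 7.1 words it, the date can move from week 8 to week 12, that is 12 − 8 = 4 weeks later.

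**5. Definite union.** Three combinations reach 13 without four bridging cortices: 4-4-3-2 (13), 4-4-4-2 (14) and 4-4-4-1 (13). The last is definite union by its total yet not healed under the primary rule.

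**6. Planning SD.** The protocol gives no SD under the cortex rule, so only a range can be shown. With 30 enrolled and 30 × 0.90 = 27 evaluable per group, power = Φ(3/(SD·√(2/27)) − 1.96):

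| Assumed SD (weeks) | Power |
|---|---|
| 3.0 | 95.7% |
| 3.4 | 90% |
| 3.5 | 88.3% |
| 4.0 | 78.7% |

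**The case against.** The strongest reply is that the governing definition is reasonably clear. Sections 7.1 and 7.1.1.1 defer to a prespecified criterion, 7.1.1.3 states it under a heading naming the primary endpoint, and the synopsis and 8.2 can be read as abbreviations. That is fair for the event. It does not rescue the scheduling rules, which are operational instructions and will be followed as written. Section 7.3 could be read as keeping films going for a child who has not met 7.1.1.3, but it contradicts 6.2.8 rather than overriding it.

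A second reply is that interval censoring accepts wide intervals. This stands in part. In a simulation of the Weibull analysis (assumed mean 8, SD 3, 27 per arm, no true difference), events in (6,8] or (8,10] were recorded as (6,12] or (8,12] for 0% to 100% of such children in both arms. The difference in medians stayed within 0.07 weeks of zero, and its standard error stayed at 0.75 to 0.81. With half affected in one arm only, the shift was about 0.26 to 0.32 weeks. The simulation picked affected children at random, so it does not test skipping that depends on the healing reading.

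Four stronger readings are tempting, and the protocol does not support them:

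- Counting ordered score patterns, 58 of the 106 with a total of at least 11 fail 7.1.1.3. A reader might infer that about half of children are affected. Patterns are not equally likely, and no patient frequency is given.
- A six-week interval might be set against the three-week margin. One child's interval width and a difference between groups are not comparable.
- A reader might infer that skipping differs by arm, because clinical care uses unedited films (6.3.7.2). No section says who scores mRUS for scheduling, the synopsis has masked films read during the study, and 6.3.7.4 lists follow-up clinicians as blinded. It is a possibility, not a finding.
- The sample size might be called too small. The direction of any SD error is unknown, and 8.2.7 raises enrolment to 30 per group partly for SD uncertainty.

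**Conclusion.** The inconsistency is real and concerns the primary endpoint. The two definitions disagree for six of the 15 score combinations totalling at least 11, always in one direction: sufficient for scheduling, but not an event. For an affected child, the scheduling text as written removes the 8- and 10-week films (or the 10-week film alone) and contradicts sections 7.3 and 8.3.6.

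How many children this touches cannot be derived from the protocol. Because a cortex scored 4 is needed, it may be few, and no material bias in the treatment difference has been shown.

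The definite-union sentence is wrong as stated, but it affects only the supportive threshold and its sensitivity analysis. Whether the planning figures match the analysed event is an open question. If the pilot used the total alone, its healing times can only be as early as or earlier than under 7.1.1.3, while the SD could be larger or smaller.

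**What to change.** - Use the 7.1.1.3 criterion in both synopsis entries, in 6.2.8 to 6.2.10 and in 8.2, and correct the cross-reference in 7.1 to 7.1.1.3.
- Reconcile the scheduling text with 7.3 so that the 8- and 10-week study films are taken unless every fractured bone meets that criterion.
- State in 8.2.2 which definition produced the pilot median and the planning SD. If it was the total alone, re-score the pilot films (18 fractures) under 7.1.1.3 and restate both.
- For definite union, either require all four cortices to score at least 3 in addition to the total of 13, or delete the claimed correspondence.

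The cost is wording, possibly a re-read of the pilot films, and a few extra 8- or 10-week visits. At the protocol's own 0.002 mSv per two-view examination (9.3.1), two additional examinations add about 0.004 mSv. Enrolment is planned to start in May 2026. Settling this beforehand matters because skipped films cannot be recovered, and choosing a definition after data exist would invite criticism of the primary result.
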